## Introduction

Invasive intracranial pressure monitoring takes on essential importance in patients with traumatic brain injury and in all cerebral pathologies in which intracranial hypertension is the main cause of death.

The dose of intracranial pressure (ICP), meant as the time for which intracranial pressure exceed the reference values, has been related to poor outcome. “Time is brain” is a concept which highlights the importance of preempt and perform the proper therapeutic strategies, in order to reduce complications in the context of a rapidly and irreversibly compromised cerebral tissue as a result of a brain injury.

On these bases, it is essential to perform an accurate intracranial pressure monitoring as soon as possible, to detect and possibly treat intracranial hypertension, which would definitively compromise brain parenchyma.

Invasive intracranial pressure monitoring performed by placing an intracerebral catheter (intraventricular or intraparenchymal) is currently the gold standard technique for continuous ICP invasive monitoring.

This maneuver has usually been performed by neurosurgeons, but in an effort to optimize as much as possible the timing of ICP monitoring, reducing time between urgent request for invasive ICP monitoring placement and the placement itself, this procedure (specifically intraparenchymal catheter placement) has more often been carried out by intensive care physicians at the bedside, in the last few years.

In the setting of clinical practice, multidisciplinary management of intracranial pressure handling and treatment is therefore achieved by joint decisions between neurosurgeons and intensive care physicians, but differences in logistic matters and in the executive availability could impact on the dose of intracranial pressure to which patient is exposed.

The aim of this study is to compare timing of invasive intracranial pressure monitoring placement performed by intensive care physicians and neurosurgeons and to detect possible differences in the incidence of complications between the two groups.

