## **Aim of the study**

### Primary outcome:

- To compare timing of invasive intracranial pressure monitoring performed by intensive care physicians and neurosurgeons, from time T1 (defined as the moment in which invasive intracranial pressure monitoring indication is stated) to time T2 (skin incision).

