## Materials and methods

Inclusion criteria:

- All patients with acute cerebral pathology with urgent indication to invasive intracranial pressure monitoring (intraparenchymal and intraventricular)
- Age greater than or equal to 18 years

Exclusion criteria:

- Patients in whom indication to intraventricular catheter placement is stated for reasons other than the need of ICP monitoring (e.g. CSF drainage)
- Patients in whom indication to invasive intracranial pressure monitoring is not an urgent request
- Patients in whom a significant coagulation disorder is a contraindication for procedure

Timings are defined as:

[figure not shown]
- T0: suspect of pathology at risk for developing intracranial hypertension
- T1: neurointensive and neurosurgical indication to invasive ICP monitoring (it could be the time when brain CT is performed or, in the absence of a brain CT, the time at which indication to invasive ICP monitoring is stated)
- T2: skin incision at skull for BOLT/EVD placement

Place of positioning:

The place (intensive care unit or operating room, specifying if it's a dedicated OR or a surgical unit) where the procedure is carried out must be declared.

Complications which will be analyzed:

- Catheter-related intracranial bleedings, with or without the need of neurosurgical operation (all the patients enrolled in the study must have been screened for coagulation disorders)
- Meningitis (actually related to procedure), with microorganism causing meningitis demonstrated by culture (not a contaminant microorganism)
- Wrong positioning of catheter and/or its malfunction (e.g., a correct placed catheter penetrates the parenchyma for few millimeters/absence of ICP wave). Malfunction is considered as such if it occurs up to 12 hours after placement.

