## Statistical analysis plan

Delta time in the placement of invasive ICP monitoring is assumed as  $T2-T1$ , declared in minutes.

Typology operator (neurosurgeon vs intensivist) impact on delta time will be evaluated through a multilevel model elaborated with a linear mixed model. The model will assume the center in which the maneuver is carried out as clustering factor. The place where the maneuver is carried out (intensive care unit vs operating room) and the confidence in performing the procedure (routine vs sporadic, defined as less than 5 times a year) will be assumed as covariates.

The incidence of complications, valued as a binary variable, will be evaluated through logistic model GLMM (generalized linear mixed model) with the organization exposed in the dedicated data element.

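### The operator comparison adjusts only for place and confidence, so a difference between operators in the time of indication could bias the primary estimate

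*Combined protocol and SAP*

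**What the plan says.** The Statistical analysis plan section sets out the primary analysis: "Typology operator (neurosurgeon vs intensivist) impact on delta time will be evaluated through a multilevel model", fitted as a linear mixed model. On clustering: "The model will assume the center in which the maneuver is carried out as clustering factor". The covariates are given in one sentence: "The place where the maneuver is carried out (intensive care unit vs operating room) and the confidence in performing the procedure", the latter split into routine and sporadic (fewer than five procedures a year). No other covariate, stratifier or sensitivity analysis is named for this model.

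No section describes how a patient comes to be treated by one operator or the other. The 1:1 split within centre appears only as an assumption under Sample size assessment, which adds that the real configuration cannot be evaluated.

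Materials and methods admits "All patients with acute cerebral pathology with urgent indication to invasive intracranial pressure monitoring", so diagnoses are mixed. It defines T1 as the point of indication (which may be the time of the brain CT) and T2 as skin incision. The Introduction notes that between the two specialties "differences in logistic matters and in the executive availability could impact on the dose of intracranial pressure to which patient is exposed".

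**The concern.** Without an allocation procedure, the operator has to be treated as an observed exposure. Who is available plausibly depends on the hour and the day, and so may the delay to incision. The random centre effect deals with stable differences between centres. It does not deal with differences within a centre by shift or by diagnosis.

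The two planned covariates do not fill that gap. Place is declared for each procedure and may carry some of the logistic delay, but it may also follow from who does the procedure. Confidence describes experience with the procedure. Neither records when the indication arose.

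Time of T1 comes before the operator is chosen, so it is not a step on the path from operator to delay, and adjusting for it does not remove a genuine operator effect. What is at stake is the primary contrast: part of an observed difference could reflect when each group was called, and the bias could favour either operator.

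**Working it through.** **Inputs from Sample size assessment.** Effect 20 minutes; between-centre and within-centre SD 10 minutes each; 16 equal centres; 64 patients, 32 per operator; significance level 5% (taken as two-sided); stated power at least 95%.

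**Inputs that are assumptions.** The documents give no out-of-hours share and no out-of-hours delay. I take a delay D of 10-20 minutes and a gap g of 10-20 percentage points in out-of-hours share between operators, with shares centred on one half (55% v 45%, 60% v 40%).

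**Step 1: the plan's own figure.** With operators balanced within centre, the centre effect cancels. SE = √(2 × 10² / 32) = 2.5 minutes, and 20 / 2.5 = 8, so power exceeds 99.99%. With the total SD √(10² + 10²) = 14.14, power is 99.99%. The claim of at least 95% is met. Power gives no protection against bias: with an SE of 2.5, an observed difference of about 1.96 × 2.5 = 4.9 minutes is already significant.

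**Step 2: how large a delay fits the planned SD.** An omitted out-of-hours indicator with share p contributes D² × p(1−p) to the within-centre variance. The planned SD is stated without any such split, so I take 10² = 100 as the full variance, which must already contain this part. At 60% v 40%, p(1−p) = 0.24, so D ≤ 10 / √0.24 = 20.4 minutes. At 55% v 45%, p(1−p) = 0.2475, so D ≤ 20.1 minutes. The delay is therefore capped near 20 minutes when the shares are near one half. A 30-minute delay at 60% v 40% would by itself contribute 900 × 0.24 = 216, more than twice the whole planned variance.

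**Step 3: bias and type I error when the true operator effect is zero.** Bias = D × g. Type I error = Φ(bias/2.5 − 1.96) + Φ(−bias/2.5 − 1.96).

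| Delay D (min) | Gap g | Bias (min) | Share of 20 min | Type I error |
|---|---|---|---|---|
| 10 | 0.10 | 1 | 5% | 7% |
| 10 | 0.20 | 2 | 10% | 13% |
| 20 | 0.10 | 2 | 10% | 13% |
| 20 | 0.20 | 4 | 20% | 36% |

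A simulation of 16 centres with 4 patients each, holding the within-centre variance at 100, gave the same rates (7%, 12%, 13% and 36%). With no gap between operators there is no bias.

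**Step 4: cost of adjustment.** Within centres there are 64 − 16 − 1 = 47 degrees of freedom. One binary covariate for T1 timing and one for diagnosis use two of them.

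**The case against.** The strongest reply is that nothing in the documents shows the bias exists. It needs time of indication to differ by operator within a centre and also to affect T2-T1, and neither link is documented. This stands: the point is about what the coefficient can absorb. A reader might infer that the operator effect does absorb out-of-hours delay, or that the protocol says availability drives the delay. The Introduction says only that such differences could affect the pressure dose.

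A second reply is that availability is part of what is being compared. That is fair, but adjusting for T1 timing compares operators called in the same time window. If neurosurgeons were slower at night, that would still count towards the operator coefficient. An additive term would not, however, show whether the operator effect itself differs by time of day.

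Third, the illustration ignores place and confidence, which are in the model. The relevant gap is the one left after conditioning on centre, place and confidence, and it may be smaller.

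Fourth, collection is not documented. For T1 this is mostly answered, since an interval in minutes needs a clock time at each end; weekend or holiday status also needs the date. For diagnosis the reply carries more weight. Diagnosis must be known to apply the inclusion criterion, but no section shows that it is coded or links it to delay. Eligibility is also limited to urgent indications and the interval starts at indication, which narrows the scope for case-mix delay.

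Device type is absent from the primary model too, although the Introduction associates intensivists with intraparenchymal catheters. That is a further matter and does not weaken this one.

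**Conclusion.** The concern holds as a conditional one. The covariate set is fixed in the plan, it leaves out a factor that precedes the choice of operator, and a better set is cheap to specify. Under the stated assumptions the bias is about 1-4 minutes, or 5-20% of the 20-minute effect, in unknown direction, with a type I error of about 7-36%. These figures rest on assumed delays and shares, on shares near one half, and on reading the 10-minute SD as the full within-centre SD. The case for T1 timing is firmer than the case for diagnosis, whose effect is not quantified here.

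Stronger readings are tempting but not supported:

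- A reader might take delays of up to 60 minutes and infer a bias of 12 minutes, or 60% of the effect. Delays that long do not fit the planned SD; they would mean that the SD itself is too small.
- A reader might infer that adjustment would cut the SE from 4.4 to about 2.6 minutes. The 4.4 comes from adding out-of-hours variance on top of the planned SD. On the plan's own SD the unadjusted SE is already 2.5.
- A reader might extend the point to the complications model. The plan refers the structure of that model to a data element that is not shown, so no conclusion can be drawn.

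**What to change.** In the Statistical analysis plan, add T1 timing to the primary linear mixed model as a prespecified fixed covariate: weekday daytime versus night, weekend or holiday, derived from the date and clock time of T1. Define the hours and the holiday calendar before analysis. Add diagnosis group, for example traumatic versus non-traumatic, where it is recorded, with the categories also fixed in advance. Report the currently planned set (place and confidence only) as a sensitivity analysis, so that readers can see how far the operator estimate moves.

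The cost is a few lines of SAP wording, about two of roughly 47 within-centre degrees of freedom, and possibly one or two extra fields if date, clock time or diagnosis is not already entered.

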### Sample size assessment

Sample size assessment has been performed by Monte Carlo simulation ( $B=500$ ). Assuming a timing decrease ( $T2-T1$ ) of 20 minutes in the procedure carried out by an intensivist compared to a neurosurgeon, with a mean time of 100 minutes, a standard deviation between center and intra-center of 10 minutes, 16 centers, each one with the same number of patients and a balance 1:1 between the two groups (intensivist:neurosurgeon), a total number of 64 patients (32 treated by intensivists and 32 by neurosurgeons), it allows to evaluate the interest effect with a power of at least 95%, and a significance level of 5%.

This elevated power has been decided according to the simplicity of the assumed design (same number of entities and conditions for center) and not evaluable in his real configuration.

## Time-line
